## 7.2.4 TWO WEEKS POST-ACTIVATION

The two-week follow-up visit will occur 1.5 to three weeks following activation of the audio processor. All audiometric testing should occur in a sound-treated booth in the sound field, with the subject seated one meter from the speaker. During soundfield measures, the contralateral ear should be plugged or masked as needed, taking special consideration for unilateral conductive or mixed hearing losses. In the case of bilateral implantation, each ear should be tested separately.

Testing should occur with the SAMBA Audio Processor and be completed prior to making programming changes to the subject's processor. Testing should be conducted using the patient's preferred program and volume settings. The following testing should be completed:

- Aided audiogram, soundfield
  - o Soundfield thresholds (500 4000 Hz) in the individual implant ear(s) alone
  - Contralateral ear plugged or masked, as needed

Programming of the SAMBA Audio Processor should be completed in accordance with the recommendations in the IFU for SYMFIT software.

## 7.2.5 ONE MONTH POST-ACTIVATION

The one-month follow-up visit will occur three to six weeks post-activation. All audiometric testing should occur in a sound-treated booth in the sound field, with the subject seated one meter from the speaker. Speaker output should be calibrated prior to conducting study-related testing to ensure consistency across study sites. During soundfield measures, the contralateral ear should be plugged or masked as needed, taking special consideration for unilateral conductive or mixed hearing losses. In the case of bilateral implantation, each ear should be tested separately.

Testing should occur with the SAMBA Audio Processor and be completed prior to making programming changes to the subject's processor. Testing should be conducted using the patient's preferred program and volume settings. The following testing should be completed:

- Aided speech testing in noise, soundfield
  - AzBio Sentences in noise at 60 dB SPL with an SNR of +5 dB
  - Speech and noise will be presented at 0° azimuth
  - One list of 20 sentences will be presented to the individual implant ear(s) alone
  - Lists will be randomized at each clinical trial site
  - o Contralateral ear plugged or masked, as needed
- Aided speech testing in quiet, soundfield
  - o CNC Words in quiet at 60 dB SPL
  - o One list of 50 words will be presented to the individual implant ear(s) alone
  - Lists will be randomized at each clinical trial site
  - o Contralateral ear plugged or masked, as needed
- Aided signal-to-noise ratio testing, soundfield
  - QuickSIN at 60 dB SPL in the individual implant ear(s) alone
  - Speech and noise will be presented at 0° azimuth
  - Lists will be randomized at each clinical trial site
  - o Reported as a signal-to-noise ratio loss
  - o Contralateral ear plugged or masked, as needed

Programming should be completed according to the IFU for SYMFIT software.

## 7.2.6 THREE MONTHS POST-ACTIVATION

The three-month follow-up visit will occur 10 to 14 weeks post-activation. All audiometric testing should occur in a sound-treated booth in the sound field, with the subject seated one meter from the speaker. Speaker output should be calibrated prior to conducting study-related testing to ensure consistency across study sites. During soundfield measures, the contralateral ear should be plugged or masked as needed, taking special consideration for unilateral conductive or mixed hearing losses. In the case of bilateral implantation, each ear should be tested separately.

Testing should occur with the SAMBA Audio Processor and be completed prior to making programming changes to the subject's processor. Testing should be conducted using the patient's preferred program and volume settings. The following testing should be completed:

- Aided speech testing in noise, soundfield
  - AzBio Sentences in noise at 60 dB SPL with an SNR of +5 dB
  - Speech and noise will be presented at 0° azimuth
  - One list of 20 sentences will be presented to the individual implant ear(s) alone
  - Lists will be randomized at each clinical trial site
  - Contralateral ear plugged or masked, as needed
- Aided speech testing in quiet, soundfield
  - CNC Words in quiet at 60 dB SPL
  - One list of 50 words will be presented to the individual implant ear(s) alone

- o Lists will be randomized at each clinical trial site
- o Contralateral ear plugged or masked, as needed
- Aided audiogram, soundfield
  - o Soundfield thresholds (500 4000 Hz) in the individual implant ear(s) alone
  - o Contralateral ear plugged or masked, as needed
- Aided signal-to-noise ratio testing, soundfield
  - o QuickSIN at 60 dB SPL in the individual implant ear(s) alone
  - o Speech and noise will be presented at 0° azimuth
  - o Lists will be randomized at each clinical trial site
  - o Reported as a signal-to-noise ratio loss
  - o Contralateral ear plugged or masked, as needed
- Subjective questionnaires
  - o SSQ12 & HDSS

Programming should be completed according to the IFU for SYMFIT software.

# 7.2.7 SCHEDULE OF EVENTS TABLE

		Candidacy/ Pre-op	Surgery	Activation	2 weeks post- activation	1 month post- activation	3 months post- activation
	Informed Consent	X					
	Medical Assessment	Х					
	Surgery	V	Χ	V			
	Unaided thresholds	Х		Χ			
Implant Ear(s)	AzBio 60 dB SPL +5 dB SNR	Unaided				Aided	Aided
Implant ear(s)	CNC Words 60 dB SPL quiet	Unaided				Aided	Aided
Implant ear(s)	Soundfield thresholds	Unaided			Aided		Aided
Implant ear(s)	QuickSIN 60 dB SPL	Unaided				Aided	Aided
	SSQ12	Χ					Χ
	HDSS	Χ					Χ

(TABLE 1)

## **8** ASSESSMENT OF SAFETY

## 8.1 REPORTING OF KNOWN RISKS

The rate of occurrence of known risks will be reported and summarized for the duration of the study. Events will be reported as the number and proportion of subjects experiencing a risk.

## 8.1.1 LIST OF KNOWN RISKS

The list of known potential risks for BONEBRIDGE implantation are:

- Post-surgical displacement of the implant
- Post-surgical translocation of the BC-FMT
- Extrusion of the implant

- Skin-related issues
- Infection
- Tinnitus
- Vertigo
- Headache
- Dural erosion/compression
- CSF leak
- Meningitis
- Bleeding/hematoma or subdural hematoma
- Facial nerve injury
- Intra-operative complications, including from anesthesia
- Device failure

## 8.1.2 UNKNOWN RISKS

Any events related to the device or procedure that are not included in the list above occurring in the study population will also be summarized and reported.

## 8.2 TIME PERIOD AND FREQUENCY FOR EVENT ASSESSMENT AND FOLLOW-UP

The occurrence of an event may be brought to the attention of the investigator during study visits, interim visits, or phone conferences over the duration of the study. All events will be reported on the Risk Occurrence case report form. Information to be collected on the CRF includes: event description, date of onset, time of onset, seriousness, and the date/time of resolution (if applicable).

Investigators should record all reportable events with start dates occurring any time after the IC is obtained. Any medical condition that is present at the enrollment/baseline evaluation will not be reported as an event. If the subject's condition deteriorates at any time during the study, however, the event will be reported.

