## 4 STUDY DESIGN AND ENDPOINTS

## 4.1 DESCRIPTION OF THE STUDY DESIGN

Approximately 30 subjects will be enrolled across three centers in this single-arm, repeated measures study, where each subject serves as his or her own control. Of the 30 subjects recruited into the study, 15 subjects with mixed hearing loss and 15 subjects with conductive hearing loss will be recruited across all three sites. After enrollment/baseline assessment confirms candidacy, qualified individuals will receive a BONEBRIDGE Bone Conduction Implant. Each subject will subsequently be fit with a SAMBA Audio Processor.

Activation will occur at two weeks post-implantation. Follow-up evaluations will occur at two weeks, one month, and three months post-activation. Soundfield thresholds, as well as speech perception testing in quiet and in noise, will be measured at the follow-up intervals. Results will be compared to the pre-operative unaided condition. In addition to any complications reported on a surgical questionnaire, safety outcomes will be collected and reported as the number and proportion of subjects experiencing a known risk. The three-month interval will be considered the primary safety and effectiveness endpoint.

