## 4.2 STUDY ENDPOINTS

## 4.2.1 PRIMARY ENDPOINTS

Primary endpoints are as follows:

- 1. Comparison of AzBio sentence score in noise with the BONEBRIDGE at three months post-activation to the pre-operative unaided score. Testing will be completed in the soundfield at 60 dB SPL with a +5 dB signal-to-noise ratio (SNR). Improvement will be defined as equal to or greater than 10 percentage points.
- 2. Number and proportion of subjects experiencing known risks, as listed above in Section 2.2.1.

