- Occurrence of Known Risks: occurrence of risks should be monitored throughout the duration of the study and reported as appropriate.

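### Known-risk monitoring is required for each subject but placed in no post-operative visit or schedule row, so the primary safety proportion is open to under-counting

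*Combined protocol and SAP*

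**What the plan says.** Section 4.2.1 lists as the second primary endpoint: "Number and proportion of subjects experiencing known risks, as listed above in Section 2.2.1". Section 4.1 adds: "The three-month interval will be considered the primary safety and effectiveness endpoint". Sections 10.2.2 and 10.2.8 make this endpoint descriptive; only the AzBio change is tested.

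On how events are found, the plan has four pieces of text:

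- Section 7.1.1 introduces its list as procedures to be carried out during the study and documented for every enrolled subject. The known-risk item in that list reads: "occurrence of risks should be monitored throughout the duration of the study and reported as appropriate".
- Section 4.1 mentions a second source: "In addition to any complications reported on a surgical questionnaire, safety outcomes will be collected and reported".
- Section 8.2, whose heading promises the frequency of event assessment, says: "The occurrence of an event may be brought to the attention of the investigator during study visits, interim visits, or phone conferences". It continues: "All events will be reported on the Risk Occurrence case report form". The form holds a description, onset, seriousness and resolution.
- Section 8.2 sets the window: "Investigators should record all reportable events with start dates occurring any time after the IC is obtained". Conditions already present at baseline count only if they deteriorate.

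The content of activation, two weeks, one month and three months (7.2.3 to 7.2.6) is audiometry, speech tests, questionnaires at three months, and fitting or programming. In Table 1 the row "Medical Assessment" is marked pre-operatively only, and no row concerns known risks.

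**The concern.** A primary endpoint should have a stated method of measurement at stated times. The AzBio endpoint has one: level, signal-to-noise ratio, list length, ear and visit. The safety endpoint has an instruction to monitor, but no visit, question, examination or responsible person. A site could follow every visit section as written, wait for subjects to volunteer problems, and not clearly depart from the plan.

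This matters most for the listed risks that are found mainly by asking or looking: skin-related issues, tinnitus, vertigo and headache. Because the endpoint is descriptive, the proportion is the whole safety result. If it is low, a reader cannot tell few events from few enquiries.

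**Working it through.** **Text check.** Each place where a known-risk assessment could sit:

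| Place | Content | Risk query or implant-site check |
|---|---|---|
| 7.2.2 Surgery | Timing, surgical steps | None; the surgical questionnaire of 4.1 is not mentioned |
| 7.2.3 Activation | Unaided audiogram, fitting | None |
| 7.2.4 Two weeks | Aided thresholds, programming | None |
| 7.2.5 One month | AzBio, CNC, QuickSIN, programming | None |
| 7.2.6 Three months | AzBio, CNC, thresholds, QuickSIN, SSQ12, HDSS, programming | None |
| Table 1 | 10 rows | None |
| 8.2 | Occasions on which an event may come to light; form for a reported event | No frequency, prompt or examination |

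The fields that 8.2 lists for the Risk Occurrence form describe an event already known. Nothing in the text says where the answer is recorded when a subject is asked and has had no event.

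**Figures in the plan.** The plan gives no expected event rate, precision target or capture rate for safety. Its only design figure, 94.2% power for AzBio (10.3), reproduces: with n = 30, a true change of 30 against a margin of 10, SD 30 and one-sided alpha 0.025, the noncentral t gives 94.16%. It has no bearing on this point.

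**Illustration.** Inputs: n = 30 (10.3). Assumed, not from the documents: the true proportion p of subjects with a given risk, and the chance s that an affected subject is recorded.

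- Expected recorded proportion = p × s. Since s cannot exceed 1, missed events can only lower it.
- Chance of recording none = (1 − p × s)^30. With p = 0.10:
  - s = 1: 0.90^30 = 0.042
  - s = 0.75: 0.925^30 = 0.096
  - s = 0.50: 0.95^30 = 0.215
- Expected count with p = 0.20: 30 × 0.20 × s = 6.0, 4.5 and 3.0 subjects at s = 1, 0.75 and 0.50.
- If 0 of 30 is recorded, the exact two-sided 95% upper limit is 1 − 0.025^(1/30) = 11.6%. That limit applies to the recorded proportion. For the true proportion it becomes 11.6/0.75 = 15.4% at 75% capture and 11.6/0.50 = 23.1% at 50%.

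**The case against.** The strongest reply is that monitoring is already required. Section 7.1.1 makes it a procedure to be performed and documented for each subject, 4.1 adds a surgical questionnaire, and 8.2 tells investigators to record all reportable events. Section 8.2 lists occasions on which events may surface; it does not say that events are left to be volunteered. The case report forms are not in the documents and may already prompt at each visit. Absence from Table 1 is weak evidence, since programming also has no row. Section 9 provides for a full review of records for missing entries.

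Much of this stands, and it rules out several stronger readings that a reader might draw:

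- *That the endpoint depends on spontaneous reports alone.* Sections 7.1.1 and 4.1 say otherwise.
- *That events will be under-counted, or that capture differs between sites.* Neither is shown. A site may ask at every visit under 7.1.1.
- *That no negative answer is ever recorded.* This cannot be known without the forms.
- *That safety is co-primary in the testing sense.* It is listed as primary but is not tested, so no alpha, power or decision rule changes.
- *That the illustrated loss applies to every listed risk.* Meningitis, CSF leak or facial nerve injury are unlikely to be missed as often as headache or a skin problem.

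The reply does not close the gap. Programming has no row, but the follow-up visit sections do call for it; known-risk review appears in neither place. The questionnaire is mentioned only in 4.1, for complications, and nothing repeats it at follow-up. A review for missing entries finds no gap where no event form was opened.

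**Conclusion.** The point holds in a limited form. The plan requires known-risk monitoring for each subject but does not say how, by whom or at which visits. Ascertainment of the second primary endpoint is therefore not standardised across the three sites and is open to under-counting. The direction follows from the text: missed events can only lower the proportion. The size is unknown. The 4%, 10% and 21% chances of recording no case rest on an assumed true rate of 10% and assumed capture of 100%, 75% and 50%, and they show scale only. The practical consequence is that a low or zero count could not safely be read as evidence of safety. This should be corrected, but it does not affect the AzBio analysis.

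**What to change.** Add a row named Known-risk review to Table 1, marked at Baseline, Surgery, Activation, 2 weeks, 1 month and 3 months, with a matching bullet in each of 7.2.1 to 7.2.6.

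- At baseline, record existing tinnitus, vertigo, headache and similar conditions, so that later only new or worsened ones count, as 8.2 requires.
- At each review, staff ask about the patient-reportable items in 8.1.1, look at the implant site while the processor is off, and record yes or no per item.
- Items that asking or looking cannot establish, such as dural erosion or BC-FMT translocation, are recorded as known or not known from clinical records, with no added tests.
- Any new or worsened yes opens the Risk Occurrence form. Spontaneous reports between visits are kept.
- Keep all implanted subjects as the denominator and report the number with a completed review at each visit. Restricting the denominator to completed reviews could drop a subject who had an event and then withdrew, since 5.4.2 ends data collection at withdrawal.
- Report the proportion with an exact confidence interval.
- Reconcile the two risk lists: the endpoint cites 2.2.1, whose bullets omit device failure (it appears in the text below them), while 8.1.1 lists it.

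If an existing form already prompts at each visit, it is enough to cite it in 8.2 and Table 1.

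The cost is one checklist page and a few minutes at visits that already take place. The downside is that the reported event proportion will probably be higher.

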## STATEMENT OF COMPLIANCE

The trial will be carried out in accordance with Good Clinical Practice (GCP), as required by the following:

- United States Code of Federal Regulations (CFR) applicable to clinical studies (21 CFR Part 50, 21 CFR Part 54, 21 CFR Part 56)
- Good Clinical Practices

All investigators involved in the conduct of this study will be informed about their obligations in meeting the above commitments.

PROTOCOL SUMMAR	Υ
Title:	Outcomes in Adults with Mixed or Conductive Hearing Loss Implanted
	with the BONEBRIDGE
Study Description:	Approximately thirty subjects with mixed or conductive hearing loss,
	meeting FDA-cleared candidacy criteria for the BONEBRIDGE, will be
	implanted and followed for three (3) months post-activation to assess
	safety and effectiveness of the BONEBRIDGE implant.
Objectives:	Primary: To assess safety and effectiveness of the BONEBRIDGE
	implant in adults with mixed or conductive hearing loss.
	Secondary: To assess post-operative audiometric and speech
	perception outcomes with BONEBRIDGE, compared to unaided pre-
	operative performance as well as report on intraoperative experience.
Endpoints:	1. Subjects will demonstrate significant improvement in AzBio
(Primary)	Sentence score in noise in the implanted ear at three (3) months post-
	activation, compared to unaided pre-operative performance.
	2. Safety data will be collected and reported as the number and
	proportion of subjects experiencing known risks of the BONEBRIDGE
(Cocondon)	implant through three (3) months post-activation.
(Secondary)	1. Subjects will demonstrate similar or better scores on CNC words in
	quiet in the implanted ear at three (3) months post-activation, compared to unaided pre-operative performance.
	2. Subjects will demonstrate similar or better soundfield thresholds in
	the implanted ear at three (3) months post-activation, compared to
	pre-operative unaided soundfield thresholds.
	3. Subjects will demonstrate similar or better performance on the
	QuickSIN in the implanted ear at three (3) months post-activation,
	compared to unaided pre-operative performance.
	4. Subjects will demonstrate stable bone conduction thresholds at the
	device activation interval compared to pre-operative bone conduction
	thresholds.
Study Population:	Approximately thirty (30) total subjects, 18 years of age and older, will
, .p.	be implanted across three study sites in the United States and Canada.

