A variety of surgical approaches can be used to properly place the BONEBRIDGE, and preoperative imaging is recommended in the planning of BONEBRIDGE placement. A review published in 2015 reported on five publications including 20 patients. (Zernotti & Bravo Sarasty, 2015) Surgical approaches encompassed transmastoid, retrosigmoid, and middle fossa or "above the temporal line." Patient anatomy and history of prior ear surgery can influence the decision on which surgical approach is most appropriate. Functional gain ranging from 24 to 43 dB was reported in these five publications.

As published by Sprinzl & Wolf-Magele in 2015, 29 studies reported improvements in audiological outcomes and low complication rates. (Sprinzl & Wolf-Magele, 2016) Twelve studies reporting safety outcomes showed a total of six minor complications across three studies, with nine studies reporting no adverse events through at least six months of follow-up. These studies included a wide range of demographic and surgical factors, indicating that BONEBRIDGE is safe for use in the approved population and with the recommended surgical techniques. Additionally, 11 studies demonstrated improved audiological outcomes in both short-term and long-term data, indicating that BONEBRIDGE is also effective in the approved population.

The current study proposes to collect multicenter safety and effectiveness data across North America. Audiological and surgical outcomes will be collected and reported, as well as the occurrence of any known risks with BONEBRIDGE implantation. The subject population will meet the current indication criteria and investigators will follow the recommended surgical techniques.

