#### 3 OBJECTIVES

All subjects will receive a MED-EL BONEBRIDGE Bone Conduction Implant.

The primary objective is to assess safety and effectivenss of the MED-EL BONEBRIDGE Bone Conduction Implant for adults with mixed or conductive hearing loss.

Secondary objectives will assess post-operative audiometric and speech perception outcomes with BONEBRIDGE, compared to unaided pre-operative performance as well as report on intraoperative experience.

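### Is the primary safety proportion left undefined because no start date is stated and the two risk lists differ on device failure?

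*Combined protocol and SAP*

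**What the plan says.** Section 4.2.1, item 2, defines the primary safety endpoint as "Number and proportion of subjects experiencing known risks, as listed above in Section 2.2.1". The Protocol Summary describes it as the number and "proportion of subjects experiencing known risks of the BONEBRIDGE" "implant through three (3) months post-activation", which fixes the end of the count. Section 4.1 states that "safety outcomes will be collected and reported as the number and proportion of subjects experiencing a known risk". Sections 8.1 and 10.2.2 repeat the number-and-proportion format; Section 8.1 sets the period as the whole study, and neither gives an onset limit.

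On recording, Section 8.2 says "Investigators should record all reportable events with start dates occurring any time after the IC is obtained". Conditions already present at baseline are not events unless they worsen. The case report form takes the date and time of onset. Section 7.1.1 asks that "occurrence of risks should be monitored throughout the duration of the study and reported as appropriate". Under Section 7.2.1 consent comes before any candidacy or baseline testing, and Section 7.1.2 allows up to four months from baseline to surgery.

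On the population, Section 3 states "All subjects will receive a MED-EL BONEBRIDGE Bone Conduction Implant", and the Protocol Summary speaks of about thirty subjects being implanted. On purpose, Section 2.1 says the study will report "the occurrence of any known risks with BONEBRIDGE implantation".

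Section 2.2.1 has 14 bullets, followed by a sentence naming device failure after surgery as a rare possibility. Section 8.1.1 has the same risks plus device failure as a fifteenth bullet.

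**The concern.** The proportion is the entire primary safety result; no test or other summary supports it. An endpoint with an end date but no start date can be computed in two ways. An analyst who carries the consent rule of Section 8.2 into the analysis would count a new or worsened headache, infection, vertigo, tinnitus or skin problem that arose before the operation. An analyst who starts at surgery would not.

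The lists raise a similar question. If the endpoint's reference to Section 2.2.1 means its bullets only, a device failure falls outside the primary proportion; under the list in Section 8.1.1 it falls inside. With about 30 subjects, one reclassified subject could turn a report of no known risks into a report of one. That would overstate the device's risk in the first case and understate it in the second.

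**Working it through.** **The plan's own figures.** No figure is stated for the safety proportion, so there is none to reproduce. The only design figure is the power of the AzBio test in Section 10.3. With n = 30, mean change 30, margin 10, SD 30 and one-sided alpha 0.025, the noncentrality is (30 − 10)/(30/√30) = 3.65, and the noncentral t distribution gives 94.16% against the stated 94.2%. It reproduces, and nothing in the safety count enters it.

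**Start of the count.** Three kinds of statement have to be read together.

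- Recording (Section 8.2): from consent onward.
- Reporting period (Section 8.1): the whole study.
- What is counted: risks of the implant (Protocol Summary), risks with implantation (Section 2.1), and two lists introduced as risks of implantation (Sections 2.2.1 and 8.1.1).

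The first is broader than the third but does not contradict it. Collecting from consent and summarizing implantation risks from surgery is a coherent reading of all three.

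**Which items could arise early.** Displacement, translocation, extrusion, intra-operative complications and device failure need an implant or an operation. The realistic pre-surgical candidates are five non-specific items: skin problems, infection, tinnitus, vertigo and headache.

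**Length of the pre-surgical period.** Inputs are from Section 7.1.2.

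- Surgery to the three-month visit: 2 + 10 = 12 weeks at the shortest, 4 + 14 = 18 weeks at the longest.
- Baseline to surgery, upper limit: 4 × 52/12 = 17.3 weeks.
- Pre-surgical share of the recording time at that limit: 17.3/(17.3 + 18) = 49% to 17.3/(17.3 + 12) = 59%.

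That limit is not the expected wait. The Protocol Summary puts each subject's participation at about four months, also 17.3 weeks. If that is counted from enrollment, which the text does not say, the time left before surgery is about 17.3 − 12 = 5.3 weeks with the shortest windows and none with the longest.

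**Effect on the proportion.** Assume one any-event proportion, 30 implanted subjects, and a reclassified subject with no other counted event. The step is 1/30 = 3.3 percentage points. Exact (Clopper-Pearson) 95% limits, which the plan does not call for, show the scale:

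| Count | Proportion | Exact 95% limits |
|---|---|---|
| 0/30 | 0% | 0 to 11.6% |
| 1/30 | 3.3% | 0.1 to 17.2% |
| 3/30 | 10.0% | 2.1 to 26.5% |
| 4/30 | 13.3% | 3.8 to 30.7% |

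The width of these intervals comes from n = 30 and not from the start date. A subject who also has a counted event after surgery changes nothing.

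The documents give no background rate. If the chance of a pre-surgical listed event were 2%, 5% or 10% per subject (assumed values), the expected numbers among 30 would be 0.6, 1.5 and 3.0. Such events might therefore occur, but each would carry an onset date before surgery.

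**By-type reporting.** Sections 8.1 and 10.2.2 do not say that the proportion is a single composite; their wording also fits a table with one row per risk. In that layout an early headache affects only the headache row, and device failure has its own row whichever list is used.

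**Device failure.** The endpoint cites Section 2.2.1 as a section. That section, headed as known potential risks, names device failure in its text, and Section 8.1.1 lists it. Counting it satisfies both. If it were left out of the proportion, Section 8.1 would still require it to be reported.

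**The case for a change.** The strongest case for a change is that an implied intention does not specify a primary endpoint. Section 8.1.2 limits unlisted events to those related to the device or procedure, but no such limit is written for listed risks, and the form contents named in Section 8.2 do not include relatedness. Section 4.1 speaks of subjects enrolled and gives the implant only to those whose candidacy is confirmed, so the denominator is also implied and not stated. A sentence or two would settle this before data are seen, at almost no cost.

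The textual points are correct: no sentence puts the start at surgery, and the two lists do differ by one bullet. The consequence does not follow to the same degree. The missing relatedness field matters little when the onset date alone separates pre-surgical from later events. The denominator is answered by Section 3 and the Protocol Summary, which describe implanted subjects. A definition counting subjects with at least one event from the start of surgery would bring in choices of its own: it would impose a composite the plan does not state, and it could leave events at induction of anesthesia unclear although anesthetic complications are on the list.

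**Conclusion.** No change follows. The missing start date is a gap in detail that the description of the endpoint largely fills: the risks counted are those of implantation, in implanted subjects, through the three-month visit. The difference over device failure is a clerical mismatch between two lists whose sections agree in substance. The safety result is descriptive, with no test, threshold or comparator, so alpha, power and the effectiveness conclusion are untouched.

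The most that one reclassified subject can do is move an any-event proportion by 3.3 percentage points, and only if that subject has no other counted event. This rests on 30 implanted subjects and a single composite; under by-type reporting the effect is confined to one row. How many subjects might be affected cannot be derived from the documents. The conclusion also relies on onset dates being completed as Section 8.2 requires, which lets a pre-surgical event be identified and shown separately.
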